6.2.5 Pre-specified Subgroups Analysis

Subgroup analysis of the primary outcomes are planned to assess effect modifiers, specifically:

- ξ Age (under 2 months, 2 – 12 months, 13 – 59 months) – as recorded at Day0
- ξ Sex (male, female) – as recorded at Day0
- ξ Presentation with cough or difficulty breathing (yes, no) – as recorded at Day0
- ξ Location (urban/rural)

Effect modification will be assessed by incorporating an interaction between the time period and the potential effect modifier in the model, acknowledging that power will be low. Stratified model results will only be presented if the interaction term is significant, defined as p-value<0.2.

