6.4 Outcomes

6.4.1 Quasi-experimental pre-post study

Two primary outcomes will be assessed between the pre-intervention and post- intervention period:

- ξ Proportion of children referred by a primary care healthcare provider to a higher level of care (either to a hospital or to an inpatient part of a larger primary healthcare facility) at Day 0 consultation
- ξ Proportion of children prescribed an antibiotic at Day 0 primary care consultation

These two outcomes are selected to reflect the intended impact on referral of children with severe disease (pulse oximetry and CDSA) and antimicrobial stewardship (CDSA). Severe complication outcomes are included in secondary outcomes rather than primary as, given the pre-post nature of the study, change in mortality / morbidity outcomes could be influenced by other events occurring between the baseline and post-intervention comparison phase.

Secondary outcomes:

- ξ Proportion of children with a severe complication (death or secondary hospitalisation) by Day 7
 - Secondary hospitalisation refers to any delayed hospitalisation (occurring at any point greater than 24 hours after Day 0 consultation) and any hospitalisation occurring without referral. The denominator is all enrolled children
- ξ Proportion of children admitted to hospital within 24 hours of the Day 0 primary care consultation and as a result of a referral
 - This is used as a proxy for 'appropriate referral' of children, as those with severe disease should generally be admitted to hospital. The denominator for this outcome is also all children enrolled in the study, rather than only referred children. This is because the proportion of referred children that are admitted may be high in routine care, in the context of an inappropriately low referral rate. The aim of the intervention is therefore to increase the overall referral rate of children with severe disease. Hospital admission is chosen as the proxy of severe disease rather than using primary care classification of severe disease, as there are inadequacies in the classification of severe disease in routine practice
- ξ Proportion of children who completed referral as reported at day 7 follow-up
- ξ Proportion of children cured (defined as caregiver reported recovery from illness) at Day 7 follow-up

Sub-groups for analysis of primary and secondary outcomes:

- ξ Age (under 2 months, 2 – 12 months, 13 – 59 months)
- ξ Sex
- ξ Presentation with cough / difficulty breathing

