4 STATISTICAL PRINCIPLES

4.1 Confidence Intervals and p-Values

Results estimates of primary and secondary outcomes will be presented along with the associated two-sided 95% confidence intervals.

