6 ANALYSIS

Analyses will be performed and reported overall and by country.

Outcomes will be presented separately for young infants (<60 days) and older children (60 days-59 months), the malaria-related outcomes will be presented only on older children.

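### Stratified subgroup results are displayed only when their own interaction p-value is below 0.2, so inconclusive strata go unshown and displayed interactions are exaggerated on average

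*SAP*

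**What the plan says.** SAP 6.2.5 opens with "Subgroup analysis of the primary outcomes are planned to assess effect modifiers, specifically" and lists four variables: age in three levels (under 2 months, 2–12 months, 13–59 months), sex, presentation with cough or difficulty breathing, and urban or rural location. Effect modification is tested by a period-by-modifier interaction, "acknowledging that power will be low". The display rule follows: "Stratified model results will only be presented if the interaction term is significant, defined as p-value<0.2".

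Other places bear on it:

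- SAP section 6: "Analyses will be performed and reported overall and by country". It also says "Outcomes will be presented separately for young infants (<60 days) and older children (60 days-59 months", with no p-value condition.
- SAP 4.1: "Results estimates of primary and secondary outcomes will be presented along with the associated two-sided 95% confidence intervals". This general rule does not say that subgroup estimates are shown whatever the interaction test gives.
- SAP 6.4 presents the primary outcomes by adherence and indication group, also without a condition.
- Protocol 6.4.1 has a list under "Sub-groups for analysis of primary and secondary outcomes" (age, sex, cough or difficulty breathing) with no reporting condition. Protocol 7.3.1 plans the interaction approach; its only condition is that the variable be balanced between periods.

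Neither document says that stratum estimates, or the interaction estimates and p-values, are reported regardless of result.

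**The concern.** Whether a pre-specified result is displayed should not depend on what it turns out to be. A filter on the interaction p-value does two things. It removes strata whose comparison is inconclusive, although with low power a p-value of 0.2 or more is weak evidence that effects are similar. And it keeps interactions that happened to come out large, so those that appear overstate the difference between strata on average.

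These subgroups matter to the study. Protocol 3.1 calls it critical to learn for which children, and in which contexts, pulse oximetry has an impact. Protocol section 4 makes characteristics associated with uptake and impact an objective. Age under 2 months and cough or difficulty breathing are themselves criteria for pulse oximetry use in Protocol 6.3. Similar effects across such strata would inform scale-up too, and the rule would leave that finding unshown.

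**Working it through.** **The plan's own figure.** The documents give no power or error rate for the subgroup tests. The only related figure is the initial sample size for referral (Protocol 6.6.1): 3% versus 4.5%, alpha 0.05, power 80%, ICC 0.005.

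- Two-proportion formula, two-sided, no continuity correction: n = 2,518 per period before clustering.
- Kenya: design effect 1 + (690 − 1) × 0.005 = 4.445; 2,518 × 4.445 = 11,193; 11,193 / 690 = 16.2, rounded up to 17 facilities; 17 × 690 = 11,730.
- Senegal: design effect 1 + (510 − 1) × 0.005 = 3.545; 2,518 × 3.545 = 8,926; 8,926 / 510 = 17.5, rounded up to 18 facilities; 18 × 510 = 9,180.

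Both match. The study was sized for the overall comparison, which is consistent with the SAP's remark on power.

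**How often results appear when there is no effect modification.** Inputs: 4 subgroup variables and 2 primary outcomes, so 8 tests per analysis set, with one overall test for three-level age; display threshold 0.2.

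- Expected displays: 8 × 0.2 = 1.6, leaving 6.4 of 8 unshown.
- Chance of at least one display, tests independent: 1 − 0.8^8 = 0.832.
- If the rule is applied overall, in Kenya and in Senegal: 24 × 0.2 = 4.8 expected displays. This expectation does not need independence.
- Chance that a given subgroup-outcome pair is shown in one country but not the other: 2 × 0.2 × 0.8 = 0.32, or 8 × 0.32 = 2.6 pairs expected.

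**How much is hidden, and how much the rest is inflated, when an interaction exists.** Take an interaction estimate that is normal with standard error 1 and mean t, where t is the true interaction divided by its standard error. It is displayed if its absolute value exceeds 1.28. Inflation is the mean absolute displayed estimate divided by t, from 2 million simulated draws per row.

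| t (assumed) | Displayed | Not displayed | Mean displayed size | Inflation |
|---|---|---|---|---|
| 1.4 | 55% | 45% | 2.12 | 1.5-fold |
| 1.0 | 40% | 60% | 1.98 | 2.0-fold |
| 0.5 | 26% | 74% | 1.83 | 3.7-fold |

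The value 1.4 is a reference case. A main effect with 80% power has an expected ratio of 1.96 + 0.84 = 2.80. In a 50:50 subgroup the interaction has about twice that standard error, so an interaction as large as the main effect has 2.80 / 2 = 1.40. The other two rows show smaller interactions. At t = 2.8 the result would be shown 94% of the time with inflation of 1.05, so the problem fades once an interaction is well powered.

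**After the change.** All 8 of 8 results appear per analysis set (24 of 24 over three sets), whatever their p-values.

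**The case against.** The strongest defence is that the rule is declared in advance. Variables, outcomes and threshold are fixed, 0.2 is lenient, and a reader can infer that a missing stratified table means p ≥ 0.2. The rule also does not exclude reporting the interaction p-values themselves. This stands in part: 0.2 hides fewer results than 0.05 would. But declaring a filter does not remove its selection effect, and a bare p-value gives no stratum effect or interval.

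Four stronger readings are tempting and should not be drawn.

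- *SAP section 6 contradicts 6.2.5.* It does not. Section 6 covers outcomes in two age bands; 6.2.5 covers stratified model results in three. Both can be followed. The overlap softens the point for young infants, but leaves 2–12 versus 13–59 months, sex, cough or difficulty breathing, and location uncovered. SAP 6.4 gives further partial cover, but does not isolate cough, and in Kenya pulse oximetry was indicated for all children.
- *Unshown strata are lost to later syntheses.* Protocol 9.6 commits to open access to the final anonymised datasets, so they could be recomputed.
- *The 83% measures the harm.* It is only the chance that something is displayed when nothing differs; with full reporting that chance is 100%. The harm is better seen in the share not displayed and the inflation.
- *A chance display is all but certain across both countries and the pooled data.* The calculation 1 − 0.8^24 = 99.5% assumes independence, yet the pooled test reuses the country data. It is only an upper guide.

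Sparse strata are a fair practical worry. Protocol 6.3 says young infants are a small share of attendees, referral is assumed at 3% before the intervention, and SAP 6.2.1 already anticipates convergence trouble.

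**Conclusion.** The point holds as a reporting matter. The SAP adds a result-dependent display condition that the protocol does not have, in the same section that concedes low power. Under no effect modification, about 1.6 of 8 results per analysis set would appear and 6.4 would not. For true interactions of 0.5 to 1.4 standard errors, 74% to 45% would go unshown, and those displayed would be inflated about 3.7-fold to 1.5-fold.

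The counts rest on a 0.2 error rate per test; the 83% also needs independent tests. The inflation range rests on assumed interaction sizes, a normal approximation and a single interaction coefficient, so it illustrates the mechanism and does not forecast this study's results. A reader might infer that the main findings are biased as well. They are not affected: the rule does not touch the primary comparison or the sample size.

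**What to change.** Delete the p<0.2 display condition from SAP 6.2.5. For both primary outcomes and every listed subgroup, report:

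- stratum-specific estimates with 95% confidence intervals, derived from the interaction model already planned;
- the interaction estimate and its p-value;
- a label stating that these analyses are exploratory and not adjusted for multiplicity.

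A forest plot would hold this compactly. Where a stratum is too sparse to estimate, for example referral in young infants, show the counts and say so.

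The change needs no new data and no extra participants. It costs a few table rows and the display of some imprecise, or possibly non-estimable, stratum effects.

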6.3 Missing Data

Missing values will be primarily due to children lost to follow-up and not reached at Day 7.

Primary outcomes are based on information collected at Day0 through a structured data collection process that prevents missing values due to compulsory data entry. Therefore, missing data on the primary outcomes are not anticipated.

Analysis on secondary outcomes that rely on Day 7 follow-up data will be performed assuming the best case scenario (alive and not hospitalised) for children lost to follow-up or withdrawn.

Additionally, missing data will be described by pre and post intervention period and by relevant indicators, such as referral and severe disease to visually inspect for imbalances.

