7.1.1 Quasi-experimental pre-post study

For each participant enrolled in the quasi-experimental pre-post study, data will be captured during the pre- and post-intervention periods according to the different assessments and Case Report Forms (CRFs) described in the visit schedule displayed in **Tab. 4**. A description of the variables collected in each CRF is available in the appendix.

Health facility visits

Quantitative research assistants will use an EDC mobile application to enter the research data of enrolled participants. The quantitative research assistant will collect from the caregiver screening information, information on care seeking behaviour, transport and costs, and clinical presentation and medical history. A number of in-depth sociodemographic and household variables will also be collected either as surrogate measures of household wealth, or known to be associated with health-seeking behaviour and / or child mortality (including maternal

education). Household wealth indicators were selected from DHS and other surveys in the study countries as those which best estimate wealth index that can be directly collected from the mother / caregiver and with a reasonable time vs. reliability trade-off. Data on laboratory investigations (if performed), final diagnosis, prescribed medication, referral or follow-up advice will be extracted from clinical notes and / or facility registers. Quantitative research assistants will seek clarification from healthcare providers only in cases where these variables are not clear from the records. Personally identifiable information (PII), including participant's name and date of birth, as well as caregiver's phone number and physical address, will be collected for linking data and detecting possible duplicates and carrying out the study follow-up.

During the post-intervention period, the research data of participants enrolled in the study will be linked with their CDSA consultation data. Additional information on oxygen saturation will be collected as recorded in clinical notes and / or facility registers. Pulse oximeter device savings will be cross-checked by quantitative research assistants at the end of the consultation where possible.

Follow-up

Quantitative research assistants will conduct the phone follow-up interviews using an EDC mobile application. Personally identifiable information (PII) will be used for contacting caregivers. A window of +3 days (Day 7 to Day 10) applies to Day 7.

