7.1.2 Routine data

CDSA individual consultation data

Routine individual consultation data will be recorded in the CDSA in all intervention facilities in the post-intervention period. As part of the intervention, healthcare providers will be asked to use MedAL-R during their consultations. When they do so, they will routinely enter all data necessary for the clinical management of children 0 – 59 months of age into MedAL-R. Data used within TIMCI will cover clinical presentation (including symptoms and dangers signs), medical history (including HIV and TB status if known), all physical exams and measurements relevant for clinical assessment (including pulse oximetry), and laboratory investigations. Automated recommendations from CDSA on diagnosis and child management will also be collected, as well as healthcare provider's agreement or disagreement with these recommendations and possible additional diagnoses and treatments, which will be manually entered. A description of the variables extracted from CDSA is available in the appendix.

HMIS aggregate facility data

HMIS data will include the total number of outpatient consultations – for all patients and for children 0 – 59 months of age (disaggregated by new and follow-up visit if possible) –, disease burden, and any other relevant indicators if available (such as referral rate or mortality rate), disaggregated by age and sex if routinely collected with this granularity.

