3.1.2 Study procedures

Research assistants (RAs) will screen and recruit participants in the waiting area prior to consultation (Day 0). Following children's caregiver informed consent, the RA will record participant name, contact details, sociodemographic details and reason for attendance prior to consultation. In case of critical and emergency cases, children will be seen immediately by the HCP. The clinical consultation will be conducted by HCPs, who in the post-intervention phase will have been advised to use the devices.

After consultation, the RA will extract information from clinical records, the caregiver and/or medical records and will document them in the database. This information includes final diagnosis, oxygen saturation and results of laboratory investigations, prescribed medication, referral or follow-up advice and usage of pulse oximeter and/or CDSA.

Follow-up at Day 7 will be conducted by phone by an RA. If phone follow-up fails, three attempts will be made on the subsequent three days to reach the caregiver. Community mechanisms to facilitate follow-up (such as arranging a call with a community health worker) will be used, with consent, for caregivers without access to a phone. A structured questionnaire will be administered to assess the primary and secondary outcomes, including details of any government or private hospital admission. In case of non-recovery, if the child is still at home, the study team will advise the family to return to the PHC clinic for a follow-up consultation. Refer to "Participant timeline" section of the Protocol for additional details.

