3.4 Sample Size

The sample size for the quasi-experimental pre-post study is calculated separately for each country, based on comparison between pre- and post-intervention periods. The following assumptions are used:

- ξ power 80%
- ξ alpha level of 0.05
- ξ pre-intervention referral to a higher level of care 3%, with a minimum detectable difference of 50%
- ξ pre-intervention antibiotic prescription of 60%
- ξ intra-cluster correlation coefficient (ICC) of 0.005 for referral and 0.05 for antimicrobial prescription
- ξ Kenya – estimated average cluster size of 230 children / month (assuming a cluster ratio of health centres : dispensaries 1:2, with 100 / month in dispensaries and 500 / month in health centres)
- ξ Senegal – estimated cluster size of 170 children per month

For the referral primary outcome, we therefore initially estimated requiring the following sample size:

- ξ Kenya – 17 facilities, recruiting an average of 690 children per quarter per facility, equating to 11,730 children per quarter
- ξ Senegal – 18 facilities, recruiting an average of 510 children per quarter per facility, equating to 9,180 children per quarter

For the antibiotic prescription primary outcome, this would enable a minimum detectable reduction of 18% in Kenya and Senegal.

Following lower than anticipated recruitment in the pre-intervention period, sample size calculation was revised. As a result, two additional facilities were added per country and the pre-intervention period was extended from an initially anticipated 3 months to a 6 – 8 month period. A decision was also taken to target a post-intervention sample size of at least the same as the pre-intervention sample size, as well as a minimum duration of 9 months post-intervention to allow for stabilisation over time and some seasonal overlap of pre- and post-intervention periods.

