6.1.3 Antibiotic-related outcomes

6.1.3.1 Proportion of children prescribed an antibiotic at Day 0

Information on antibiotics prescription are recorded by the RA on Day 0, after the clinical consultation. The data collection tool is structured in a way to facilitate the reporting of antibiotics, starting with single-drug questions for the most common/important ones to drop-down lists for other antibiotics/treatments and free text. All options will contribute to determine whether an antibiotic prescription was given. A child will be considered prescribed with an antibiotic if:

- ξ “Yes” was selected for at least one single-drug question
- ξ “No” was selected for all single-drug questions but one or more antibiotics were selected from the antibiotics/treatments drop-down list
- ξ “No” was selected for all single-drug questions, antibiotics were not selected from the other antibiotics/treatments drop-down list but antibiotics were listed in the free text field (conditional to feasibility of assessing free text)

All children recruited will be counted in the denominator.

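### The primary outcomes do not separate 'not prescribed / not referred' from 'no consultation or no record found', and record completeness can change when the tablet arrives; the antibiotic outcome has no check for this.

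*SAP*

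**What the plan says.** SAP 6.3 states that the primary outcomes come from a "structured data collection process that prevents missing values due to compulsory data entry" and that missing primary data are therefore not expected.

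- **Numerators.** Referral (SAP 6.1.1, 6.1.2.4) is positive only if the research assistant (RA) confirms that urgent referral advice was recorded. Antibiotic prescription (SAP 6.1.3.1) is positive only through the RA's single-drug questions, a drop-down list or free text, and the free text counts only "conditional to feasibility of assessing free text".
- **Denominators.** For antibiotics, "All children recruited will be counted in the denominator". Referral uses the same denominator (SAP 6.1.2.4). Recruitment takes place in the waiting area, before the consultation (SAP 3.1.2).
- **Source.** Protocol 7.1.1 says that "prescribed medication, referral or follow-up advice will be extracted from clinical notes and / or facility registers". RAs go back to the provider only if the record is unclear.
- **What changes with period.** In the post-intervention period providers are asked to use the tablet: "When they do so, they will routinely enter all data necessary for the clinical management of children" (Protocol 7.1.2). SAP 6.2.1 starts the post-intervention period, facility by facility, once trained providers are back and the devices have been delivered. Protocol 7.1.1 links research data to the clinical decision support algorithm (CDSA) record in that period. The SAP definitions do not say whether the CDSA record counts.
- **Checks.** SAP 6.2.4 plans two alternative referral definitions that use caregiver report. It plans no alternative source for antibiotics.

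**The concern.** Neither definition has a category for a child who left unseen or for whom no record was found. Such a child cannot enter the numerator, so the child is counted as not prescribed and not referred. If this were equally common in both periods, it would dilute both rates and do little else. But the way consultations are charted changes on the same date as the intervention. There is no concurrent control, and none of the covariates in SAP 6.2.2 captures completeness of recording. A change in completeness would therefore be absorbed into the period effect.

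A loss of capture after the tablet arrives would lower recorded prescribing, which is the intended direction, and would lower recorded referral, which is against the hypothesis. The reader of the results would have no table from which to judge whether this happened.

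**Working it through.** **Inputs from the documents.** Antibiotic prescribing 60%; referral 3% rising to 4.5%; ICC 0.05 (antibiotic) and 0.005 (referral); power 80%; "alpha level of 0.05" (SAP 3.4); "associated two-sided 95% confidence intervals" (SAP 4.1), so two-sided. Kenya 17 × 690 = 11,730 and Senegal 18 × 510 = 9,180 children per period (Protocol 6.6.1). These are the initial sizes; no revised total is given.

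**Plan's own figures.** Two proportions, 3% v 4.5%, need 2,518 per period without clustering.
- Kenya: design effect 1 + 689 × 0.005 = 4.445; 2,518 × 4.445 / 690 = 16.2, so 17 facilities.
- Senegal: 1 + 509 × 0.005 = 3.545; 2,518 × 3.545 / 510 = 17.5, so 18 facilities.
- Antibiotic: design effects 35.45 and 26.45 give effective sizes 11,730 / 35.45 = 331 and 9,180 / 26.45 = 347. Power for 60% v 49.2% (an 18% reduction) is 79.8% and 81.7%.

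The stated sizes reproduce and are not at issue.

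**Effect of a recording loss.** Observed rate = true rate × (1 − share unrecorded). The shares are assumptions; the documents give none.

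Antibiotic, true 60% in both periods, no pre-period loss:
- 5% post loss: 0.60 × 0.95 = 57%; OR = (0.57/0.43)/(0.60/0.40) = 0.88.
- 10% post loss: 0.60 × 0.90 = 54%; OR = (0.54/0.46)/(0.60/0.40) = 0.78.
- Against the planned absolute effect of 60 − 49.2 = 10.8 points, these are 3/10.8 = 28% and 6/10.8 = 56%.

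**Chance of a false positive.** With n per period, d = |p1 − p2|, s0 = √(2p̄(1 − p̄)/n) and s1 = √((p1(1 − p1) + p2(1 − p2))/n), the two-sided rejection probability is Φ((d − 1.96 s0)/s1) + Φ((−d − 1.96 s0)/s1). No true change is assumed.

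| Unrecorded pre / post | Antibiotic observed | OR | Plan's design effect (Kenya / Senegal) | Design effect 1 (Kenya / Senegal) |
|---|---|---|---|---|
| 5% / 10% | 57.0% → 54.0% | 0.89 | 12% / 12–13% | 99.6% / 98.3% |
| 5% / 20% | 57.0% → 48.0% | 0.70 | 64% / 66% | not run |

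The two right-hand columns bracket the answer. The same facilities serve in both periods and the model has a facility random intercept, so stable differences between facilities largely cancel, which pulls towards design effect 1. Variation of the period change between facilities pushes back towards the plan's figure. The documents do not give that variation.

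**Referral.** For 5% / 10% unrecorded, 2.85% → 2.70% (OR 0.95) gives 6% false positives under the plan's design effect and about 10% at design effect 1. The larger risk is masking: for a true 3% → 4.5% rise, Kenya's power falls from 82% to 67% (5% / 10%) or 34% (5% / 20%).

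**Recording alone.** To produce the whole planned effect, post-period capture would have to be 0.82 times pre-period capture for antibiotics, or 1.5 times for referral.

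**The case against.** The case against has force on several points.

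- A reader might infer that the tablet does reduce what reaches the notes. No passage says so. Notes and registers remain the stated source after the intervention, and training and supervision could improve recording.
- A reader might infer that the source is a single paper entry. It is wider: health card, referral note, ledgers, medical records (Protocol 6.5.1), the caregiver (SAP 3.1.2), and the provider when a record is unclear. A child with no entry at all may prompt such a query; a legible entry with no antibiotic would not.
- A reader might infer that a recording shift could pass for success on both primary outcomes. It could not: the intended effects run in opposite directions, so a common shift favours one and hides the other.
- The form description is an appendix not available here, and other fields do have codes for unreadable or unreported results (SAP 6.1.4). How an unseen child is coded is therefore unknown. This does not rescue the definition: only affirmative routes enter the numerator, so any other code is counted as negative.
- Existing checks help in part. Supervisors compare research data with source at random (Protocol 7.2.4), and missing primary data are monitored (Protocol 8). The service provision assessments observe consultations in both periods and are linked, but the SAP defers that analysis and does not name it as validation. The caregiver-based referral analyses are uneven in Kenya, where caregiver-reported urgency exists only post-intervention (SAP 6.2.4, footnote). None of these tests antibiotic capture by period.
- The free-text rule is third in line and the same in both periods, so it is a smaller matter. It still leaves a primary outcome open to a later judgement of feasibility.

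**Conclusion.** The concern holds as a gap in the definitions and checks, not as a demonstrated bias. The statement in SAP 6.3 rests on compulsory entry alone, absent records and absent consultations are merged with true negatives, and the recording workflow changes at the boundary that defines the comparison. The antibiotic outcome is the main exposure, because its possible bias could run in the hoped-for direction and it has no alternative-source analysis.

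An assumed post-only loss of 5–10% would show as an OR of 0.88–0.78 with no true change. For 5% pre and 10% post loss, the chance of a false positive lies between about 12% and about 98–99.6%, depending on facility-by-period variation. The near-certain end should not be read as the expected result: it needs both an assumed differential loss and no such variation. Recording alone would produce the full planned 18% reduction only with an 18% relative loss of capture. This is a cheap improvement rather than a flaw that invalidates the plan.

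**What to change.** 1. **Keep all recruited children as the primary denominator.** Report the number with no consultation or no source record found, by period and facility. Add a sensitivity analysis restricted to children with a located record from a source available in both periods. Do not use the CDSA to decide who has a record, because it exists only post-intervention. For example, if 5% lack a record in both periods and true prescribing is 60%, the all-recruited analysis gives 57% v 57%. A restriction that lets CDSA entries qualify gives 60% v 57% (OR 0.88), a spurious reduction.
2. **For antibiotics only, pre-specify a conservative bound.** Count a post-period child as prescribed if either the RA extraction or the linked CDSA record shows a systemic antibiotic that the provider accepted or entered. An automated recommendation alone does not count. Tabulate children positive in the CDSA but negative in the RA data, by facility, and report whether the reduction survives. For referral, tabulate the discordance only: a second source available only post-intervention would push referral in the hypothesised direction.
3. **Code free-text antibiotics in both countries and both periods, blind to period,** in place of the feasibility condition. State in SAP 6.1 which source defines each outcome in each period.

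The cost is SAP wording, some programming and coding, and linkage work that the protocol already plans. The protocol anticipated the end of data collection in Q1 2023 and SAP version 1.0 is dated 05/04/2023, so the category in step 1 may have to be derived from existing fields. Imperfect linkage would leave the bound in step 2 incomplete, so the linkage rate should be reported with it.
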